4.2 Analysis Population

All analyses on efficacy variables will use the Modified Intent-to-Treat (MITT) population as primary. A completer's population will be used as a secondary analysis population for the primary and secondary endpoints. The Intent-to-Treat (ITT) population will be used as sensitivity analysis population for proportion-based efficacy endpoints.

Intent-to-Treat Population (ITT):

This population consists of all randomized patients, who received at least 1 dose of study medication. Under this approach, patients are counted in the treatment group to which they were randomized, regardless of the treatment received during the course of the trial. In this population, missing data handling for efficacy analyses will be specified in Section 7.4.

Modified Intent-to-Treat Population (MITT):

This population consists of all randomized patients, who received at least 1 dose of study medication, have a baseline measurement, and have a post-randomization measurement. Under this approach, patients are counted in the treatment group to which they were randomized, regardless of the treatment received during the course of the trial. Note that MITT population can vary with endpoints since some patients may have the needed data for inclusion in the MITT population for some endpoints but not for others.

Completers Population (CP):

This population consists of all patients in the MITT population who completed the study. No missing data will be imputed for this analysis. Any substantial differences between conclusions based on the ITT /MITT population and the completers' population will be investigated.

Safety Population (SP):

The Safety Population will include all randomized patients who received study medication.

4.3 Approaches to Efficacy Analysis

The efficacy endpoints at Week 12 will be analysed in the ITT population using the multiple imputation (MI) method to handle missing data. See Section 7.4.1, Section 9 and Appendix 5 for details.

For all analyses, two models will be fitted. One model will be fitted for the individual treatment comparisons (APD334 2mg vs Placebo, APD334 1mg vs Placebo, APD334 2mg vs APD334 1mg) with the treatment term containing the three treatment groups, namely APD334 2mg, APD334 1mg and Placebo, and a second model will be fitted for the pooled treatment comparison (APD334 2mg & 1mg vs Placebo) with the treatment term containing two treatment groups, pooled APD334 2mg & 1mg and Placebo.

4.3.1 Primary Efficacy Analysis

The primary analysis will be based on the change from baseline in 3-component Mayo Clinic Score (consisting of subscores for stool frequency, rectal bleeding and findings of endoscopy) at Week 12 using an analysis of covariance (ANCOVA) model with terms for treatment, current oral corticosteroid use, prior exposure to TNF α antagonists and baseline value as covariate. Least-squares mean (LSM) by treatment group and its 90% confidence interval (CI), and least-squares mean difference between treatment group and its 90% CI will be reported.

4.3.2 Secondary Efficacy Analyses

The secondary analyses include the following:

- The proportion of patients who achieve endoscopic improvement will be analysed individually using Cochran-Mantel-Haenszel (CMH) test adjusted for the stratification factors of presence or absence of current oral corticosteroid therapy at baseline and previous exposure to TNF α antagonists, to compare the difference of proportions between treatment groups. The CMH stratified risk difference and its 90% confidence interval will be provided.
- The analyses based on the change from baseline in 2-component Mayo Clinic Score and Total Mayo Clinic Score at Week 12 will be performed using an ANCOVA model with terms for treatment, current oral corticosteroid use, prior exposure to TNF α antagonists and baseline value as covariate. Least-squares mean (LSM) by treatment group and its 90% confidence interval (CI), and least-squares mean difference between treatment group and its 90% CI will be reported.

[figure not shown]
4.3.3 Exploratory Efficacy Analyses

Trichotomous composite endpoint of clinical remission and clinical response at Week 12 is an ordinal categorical endpoint with 3 categories (2, 1, 0). It will be analysed using Cochran-Mantel-Haenszel method adjusted for the stratification factors of presence or absence of current oral corticosteroid therapy at baseline and previous exposure to TNF α antagonists. The testing statistic and p-value will be computed using modified ridit scores for between-treatment comparison.

[figure not shown]
For proportion based efficacy endpoints such as [REDACTED]

[figure not shown]
[REDACTED]
patients who achieve clinical remission and proportion of patients who achieve clinical response similar analyses specified for secondary analyses, such as CMH test will be performed.

[REDACTED]

Dose response analyses will be performed using an ANCOVA model for continuous variables, or logistic regression model for categorical variables, as appropriate. Treatment group and appropriate baseline covariate will be included in the analysis model. Statistical testing of dose response trend will be based on appropriate contrast statement assuming monotonic dose response profile in placebo (lowest response), APD334 low dose (middle-range response) and APD334 high dose (highest response).

4.5 Definition of Compliance Measure

Compliance will be assessed using patient data recorded in the drug accountability form of the electronic case report forms (eCRFs). On each day, a patient should take his/her assigned treatment. The compliance rate for each patient will be computed as $100\% \times (\text{actual number of tablets taken over the study period}) / (\text{designated total number of tablets that should have been taken over the study period})$. Study period is defined as the number of days that the patient has been in the active treatment phase of the trial. Compliance rates will be summarized for each treatment group.

5 SAFETY ANALYSES

Safety and tolerability will be assessed by a review of all safety parameters including adverse experiences (AEs), laboratory safety parameters, vital signs, and electrocardiogram (ECG). Only summary tabulations (N, mean [or median], SD, mean [or median] change/percent change) and 90% CIs for between-group differences will be obtained. Adverse experiences will only be presented as summary tabulations.

5.1 Safety Population

The analyses for all safety outcomes (categorical or continuous measures) will use the safety population which consists of all randomized patients who received at least 1 dose of study drug; in addition, if a patient is found to have taken a study therapy for the entire duration of the study different from that to which he/she was randomized, then the patient is counted in the treatment group of the drug he/she actually received.

For analysis based on laboratory measurements, at least 1 laboratory test post-randomization is required for inclusion in the safety population. When assessing change from baseline, a baseline measurement is also required. No missing data will be imputed for the safety analysis.

5.2 Dose and Duration

The duration of treatment for each patient will be assessed by calculating the number of weeks on drug. For each dosage, the range (minimum and maximum) of values for days on drug and the mean number of days on drug and exposure in patient-weeks will be calculated.

5.3 Adverse Events

Adverse events will be coded using the most current Medical Dictionary for Drug Regulatory Affairs (MedDRA, version 18.0 or later) and tabulated, including categorical information of interest such as onset and resolution times, time of onset relative to dose, severity at onset, maximum severity, causal relationship to study medication, and action taken. AEs will be regarded as ‘pre-treatment’ if they occur between screening and the time of administration of the first dose of APD334 or placebo and will be recorded as medical history. All other AEs that occur after the first dose of study medication will be considered to be ‘treatment-emergent’.

Treatment-emergent AEs (TEAE) will be listed by patient and by treatment. They will be summarized per treatment and expressed in terms of maximum severity and relationship to study medication. The incidence of TEAEs classified according to system organ class (SOC) will be summarized by treatment group. TEAEs will also be summarized by maximum intensity (assessed according to the Common Terminology Criteria for Adverse Events v4.03⁸ definitions) and relatedness to study medication.

Summaries of the number (%) of patients in each treatment group with at least 1 TEAE, classified according to MedDRA system organ class and preferred term, will also be provided for:

- Drug-related TEAE
- Treatment-emergent AEs leading to permanent discontinuation of study medication (study medication discontinued or withdrawal from study).
- Serious adverse events (SAEs)

Serious adverse events will be listed by patient and by treatment. If there are no SAEs at the end of the study, the tables or listings will state that there are no SAEs in the study.

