6.3 Physical and Neurological Examinations

6.3.1 Physical Examination

The physical examination include assessments of general appearance, skin, head (eyes, ears, nose, and throat), neck, thyroid, lungs, heart, abdomen, back, lymph nodes, and extremities, and body weight will be performed during [REDACTED] by the principal investigator or subinvestigator. A limited examination to assess clinically significant changes from the examination performed at screening will be completed during the [REDACTED] visit. Height will only be obtained at screening.

The physical examination will also include visual acuity and dilated ophthalmoscopy (by an ophthalmologist) and with OCT (where available) at screening and [REDACTED] visit to rule out and monitor for any significant retinal disease, including macular edema. Retinal photos will be taken during the screening visit [REDACTED] visit and any subsequent unscheduled ophthalmoscopy.

Safety ECGs will also be performed as outlined in the schedule of procedures and visits (██████).

Clinically significant findings from the physical/neurological examination performed at screening will be recorded as medical history. Any new clinically significant findings from the time of screening through the first dose of study drug will be recorded as pre-treatment AEs. After the administration of the first dose of study drug, clinically significant findings will be recorded as AEs.

[figure not shown]

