6.11.1 Adverse Event Reporting

Patients will be instructed that they may report AEs at any time. AEs that occur from ICF signature until the time of administration of the first dose of APD334 will be regarded as ‘pre-treatment’ and recorded as an AE. All events reported following study medication administration up to 30 days after the last medication intake will be presented as treatment emergent AEs (TEAEs)

Monitoring of AEs will be continued up to 30 days after study medication administration. In the event that an AE is not resolved or stabilized by this time, the sponsor in consultation with the investigator will decide whether to continue to monitor the AE or close-out the event in the database if no further follow-up is necessary.

For this study, an AE is defined as: “Any untoward medical occurrence in a study patient administered any dose of study medication (APD334 or placebo) and which does not necessarily have to have a causal relationship with this treatment.” An AE can therefore be any unfavorable and unintended sign (including an abnormal laboratory finding), symptom, or disease temporally associated with the use of the study medication, whether or not related to the product. AEs can be any of the following:

- Unfavorable changes in general condition
- Subjective or objective signs/symptoms

- Concomitant disease or accidents
- Clinically relevant adverse changes in laboratory parameters observed in a patient in the course of a clinical study
- Pre-existing conditions which worsen in severity or frequency or which have new signs/symptoms associated with them

Lymphopenia will not be captured as an adverse event both to maintain the study blind, and also because it is an expected pharmacologic effect of the drug. In order to ensure safe conduct of the study and minimize the risk of study personnel or sponsor becoming unblinded to treatment assignment, total WBC and [REDACTED] will be monitored by a central CRO physician(s) unblinded to the [REDACTED] and leucocyte counts. This person will remain blinded to the study medication

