6.11.2 Serious Adverse Events and Expedited Reporting of Adverse Events

A Serious Adverse Event (SAE) is any untoward medical occurrence that at any dose results in the following outcomes:

- Death
- Is Life-Threatening
- Required/Prolonged Hospitalization
- Disability/Incapacity
- Congenital Anomaly/Birth Defect
- Important Medical Event

SAEs will be captured from the time of ICF signature to 30 days after the last dose of study drug, and will be monitored until resolution or stabilization.

An important medical event that may not result in death, be life-threatening, or require hospitalization may be considered a SAE when, based upon appropriate medical judgment, it may jeopardize the patient and may require medical or surgical intervention to prevent one of the outcomes listed in this definition. Examples of such a medical event includes allergic bronchospasm requiring intensive treatment in an emergency room or at home, blood dyscrasias, or convulsions that do not result in in-patient hospitalization, or the development of drug dependency or drug abuse.

Elective hospitalization and/or surgery for clearly pre-existing conditions (for example a surgery that has been scheduled prior to the patient's entry into the study) will not be reported as a SAE. All other hospitalizations, including elective hospitalizations for any condition that was not pre-existing, will be reported as a SAE.

Any AE considered serious by the investigator or which meets SAE criteria must be reported to PPD Pharmacovigilance (PVG) using the remote data capture (RDC) system within 24 hours from the time study site personnel first learn about the event. The following contact information is to be used for SAE reporting:

PPD Medical Affairs/Pharmacovigilance

PPD PVG Hotline EMEA and APAC: [REDACTED]

PPD PVG Hotline NA: [REDACTED]

PPD PVG Fax line: [REDACTED]

In the event that RDC entry is not possible (e.g., system failure or access problems), the study site should complete the paper SAE report form and fax the form to PPD PVG within 24 hours of awareness of the event. The RDC system should be updated as soon as it is available.

A full description of every serious adverse event will need to be provided to PPD PVG (this may be supported by source documentation such as laboratory reports or a discharge summary should the patient be hospitalized).

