9.8.1 Adverse Events

Adverse events will be coded using the most current Medical Dictionary for Regulatory Activities (MedDRA) and tabulated, including categorical information of interest such as onset and resolution times, time of onset relative to dose, severity at onset, maximum severity, causal relationship to study medication, and action taken. AEs will be regarded as 'pre-treatment' if they occur between Screening and the time of administration of the first dose of APD334. All other AEs that occur after the first dose of study medication will be considered to be 'treatment-emergent'.

Treatment-emergent AEs (TEAE) will be listed by patients and by treatment. They will be summarized per treatment and expressed in terms of maximum severity and relationship to study medication. The incidence of TEAEs classified according to system organ class will be summarized by treatment group. TEAEs will also be summarized by maximum intensity (assessed according to the Common Terminology Criteria for Adverse Events v4.0313 definitions) and relatedness to study medication.

Summaries of the number (%) of patients in each treatment group with at least 1 TEAE, classified according to MedDRA system organ class and preferred term, will also be provided for:

- Drug-related TEAE
- Treatment-emergent AEs leading to permanent discontinuation of study medication (study medication discontinued or withdrawal from study).
- Serious adverse events (SAEs)

Serious adverse events will be listed by patient and by treatment. If there are no SAEs at the end of the study, the tables or listings will state that there are no SAEs in the study.

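### SAP 5.3 files pre-treatment adverse events as medical history, against protocol 6.11.1 and 6.3.1; pre-dose SAEs and on-treatment worsening could be misclassified

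*SAP*

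**What the plan says.** SAP 5.3 (Adverse Events) labels as pre-treatment the AEs that arise between screening and "the first dose of APD334 or placebo and will be recorded as medical history". All other AEs after the first dose are treatment-emergent.

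The protocol sends the same events elsewhere:

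- Protocol 6.11.1 takes events from signature of the informed consent form (ICF) to first dose, calls them pre-treatment, "and recorded as an AE".
- Protocol 6.3.1 separates two files. Findings at the screening examination are medical history, but: "Any new clinically significant findings from the time of screening through the first dose of study drug will be recorded as pre-treatment AEs".
- Protocol 6.11.2 on serious events: "SAEs will be captured from the time of ICF signature to 30 days after the last dose of study drug".

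For output, protocol 9.8.1 says "Treatment-emergent AEs (TEAE) will be listed by patients and by treatment" and SAP 5.3 says "Treatment-emergent AEs (TEAE) will be listed by patient and by treatment". Both sections then call for a listing of SAEs without restricting it to treatment-emergent events. Both add that, if none occurred, the outputs will say so.

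**The concern.** The analysis plan changes the file in which a class of safety events is held, and the change is not announced. The protocol monitors patients from consent for reactions to the drug and to study procedures (6.11). It also gives expedited handling to SAEs that may be linked to trial procedures (6.11.2). Every patient has a bowel preparation and a proctosigmoidoscopy during screening (6.9.1), so events before the first dose are foreseeable.

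If a programmer builds the AE dataset from SAP 5.3 as written, two things are at stake: whether a pre-dose SAE appears in the SAE listing, and whether an event that begins in screening and worsens on drug enters the TEAE counts by arm.

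**Working it through.** No arithmetic decides this point. It is settled by setting the texts side by side.

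| Question | Protocol | SAP |
|---|---|---|
| Where do events before first dose go? | AE record, labelled pre-treatment (6.11.1, 6.3.1) | Medical history (5.3) |
| When does SAE capture start? | ICF signature (6.11.2) | Not stated; the clause in 5.3 covers all AEs with no exception for serious ones |
| Which AEs are listed? | TEAEs (9.8.1) | TEAEs (5.3) |
| Is the SAE listing limited to treatment-emergent events? | No (9.8.1) | No (5.3) |
| How is an event that worsens after first dose classed? | Worsening of a pre-existing condition is an AE (6.11.1), but 9.8.1 gives no rule for a single continuing record | No rule |

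**1. Is it a real contradiction?** Yes. Protocol 8.2.1 and 9.8.1 contain nearly the same sentence as SAP 5.3 but without the medical-history clause, so the SAP added it.

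**2. Is it declared?** SAP 1.1 points to Section 9 for changes from the protocol. The readable text there covers objectives and endpoints, sample size, confidence level, the remission and response definitions, and missing data. It does not mention adverse events. Parts of Section 9 are not visible.

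**3. Non-serious events.** Neither document plans a listing of pre-treatment AEs, so the clause removes nothing that was planned. Such events might still appear in the medical history listing of SAP Section 2. That listing is not equivalent. SAP 5.3 specifies severity, causality and action taken for AEs; for medical history the documents specify only coding (protocol 8.2.3) and a listing of abnormalities.

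**4. SAEs.** SAP 5.3 contains two sentences that conflict for a pre-dose SAE in a dosed patient. The SAE listing includes it. The medical-history clause, read literally, takes it out of the AE data from which that listing would be built. If it were the only SAE, the outputs would wrongly state that there were none. The SAE summary table is unaffected, because both documents define it for patients with at least one TEAE.

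**5. Worsening on treatment.** There are two cases.

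- *The site opens a new record at worsening.* The new record starts after first dose and is a TEAE. Nothing is lost.
- *The site keeps one record.* Protocol 6.11.3 grades severity at onset and adds the maximum severity when the outcome is recorded. The record keeps its pre-dose onset, SAP 5.3 classes it as pre-treatment, and it is not counted as a TEAE.

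Neither document requires the first practice. The gap in the second case also exists under protocol 9.8.1, which uses the same split. The medical-history clause does not create it, but the SAP is where it should be closed.

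**6. Size.** Screening takes about 4 of 18 weeks (4/18 = 22%). With the 35-day extension it takes 5 of 19 weeks (5/19 = 26%). These are shares of time, not event rates. The documents give no rate of pre-dose events, so no count can be estimated.

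**The case against.** The strongest reply has four parts.

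- *A SAP does not change what sites record or report.* SAEs still go to pharmacovigilance within 24 hours (protocol 6.11.2), and the SAE listing is unrestricted as written. This stands. A reader might infer that screening-period AEs and SAEs drop out of the safety listings, but the documents do not support that. Non-serious pre-treatment events were never in a planned AE listing, and SAEs leave theirs only if the clause is carried over to serious events when the dataset is built.
- *Worsening is already covered.* Protocol 6.11.1 makes worsening of a pre-existing condition an AE, and after first dose that AE is treatment-emergent. This stands where a new record is opened. It does not settle the single-record case. A reader might infer that TEAE counts by arm are bound to be short; that too goes beyond the text.
- *The protocol is not uniform.* Protocol 6.11.1 defines an AE in a patient who has been given study medication. Sections 6.2 and 7.4 place the documentation of pre-treatment AEs within the update of history and examination. This is fair, but those sections still call the events AEs, and 6.11.1 says expressly how events before first dose are recorded.
- *Section 9 concerns planned analyses and is partly hidden.* This stands as a limit: one can say only that the readable part is silent.

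**Conclusion.** The point holds and is minor. SAP 5.3 contradicts protocol 6.11.1 and 6.3.1 on where pre-treatment AEs are recorded, and it sits badly with SAE capture from consent in 6.11.2. Efficacy estimates, alpha and power do not change.

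The effect on safety outputs is conditional and cannot be sized from the documents. The SAE listing is affected only if a dosed patient had an SAE before first dose and the clause is applied to it. TEAE counts are affected only if a screening event worsens on treatment and is kept as one record. Where neither happens, the listings and tables are the same with or without the clause. The share of participation spent in screening should not be read as the size of the problem.

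**What to change.** In SAP 5.3:

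1. Delete the medical-history clause at the end of the sentence on pre-treatment events. Keep these events in the AE dataset with a pre-treatment flag, as protocol 6.11.1 and 6.3.1 require.
2. State that the SAE listing covers events from ICF signature, with pre-treatment SAEs flagged.
3. State that a pre-treatment event that increases in severity or becomes serious after the first dose is counted as a TEAE from that date. This applies the worsening criterion of protocol 6.11.1 to the case of a single record.

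If the sponsor prefers to keep the medical-history rule, it should be declared in Section 9 with serious events excepted, and protocol 6.11.1 and 6.3.1 should be reconciled with it.

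The cost is a short change to the SAP text, one flag and a small listing, all from data that the protocol already collects. It can be done before database lock.

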5.10 Data Safety Monitoring Board

The Data Safety Monitoring Board (DSMB), independent from Arena, will be established to review safety data from this study including, but not limited to, AEs of special interest (e.g., bradycardia, infections, PML) at regular intervals and make recommendations. The roles and responsibilities of the DSMB will be outlined in a separate charter.

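### SAP 5.3 sets the all-cause TEAE incidence table at system organ class; preferred-term counts by arm are specified only for drug-related, discontinuation and serious events

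*SAP*

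**What the plan says.** SAP 5.3 describes two levels of adverse event table.

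- **All TEAEs:** "The incidence of TEAEs classified according to system organ class (SOC) will be summarized by treatment group". Protocol 9.8.1 matches: "The incidence of TEAEs classified according to system organ class will be summarized by treatment group".
- **Three subsets:** numbers and percentages of patients per arm "with at least 1 TEAE, classified according to MedDRA system organ class and preferred term, will also be provided for" drug-related TEAEs, TEAEs leading to permanent discontinuation, and SAEs.

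SAP 5.3 also plans summaries of TEAEs by maximum severity and by relatedness, without giving a MedDRA level, and a patient-level listing of every TEAE. The opening of SAP 5 confines adverse events to summary tabulations.

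Protocol 5.10 gives the DSMB the task of reviewing safety data "including, but not limited to, AEs of special interest (e.g., bradycardia, infections, PML) at regular intervals and make recommendations". No visible SAP text defines or tabulates these special-interest events. The body of SAP 5.8 (safety ECG and Holter) is not visible, and the SAP contents list has a blacked-out entry after 5.8.

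**The concern.** Organ-class totals combine many different events. A reader who wants to know how many patients per arm had one particular event, whatever its cause, needs a preferred-term table of all TEAEs, and SAP 5.3 does not specify one.

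For events that are neither serious nor treatment-ending, the only specified preferred-term count passes through the investigator's causality judgement (Protocol 6.11.4). An event judged unrelated drops out of that count. Since adverse events are to be presented only as summary tabulations, the level of those tables is the whole planned analysis of them. The trial has a safety objective and compares two doses with placebo, so a plain all-cause incidence by arm is a basic output.

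**Working it through.** The plan states no figure on this point, so the check is a comparison of texts.

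**Step 1. Which tables reach preferred-term level by arm?**

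| Set of TEAEs (SAP 5.3) | Organ class | Preferred term | Filtered by causality? |
|---|---|---|---|
| All TEAEs | yes | not specified | no |
| "Drug-related TEAE" | yes | yes | yes |
| Leading to permanent discontinuation | yes | yes | no |
| SAEs | yes | yes | no |

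Three preferred-term tables are specified, and none covers all TEAEs. The severity and relatedness summaries state no MedDRA level, so they cannot be counted either way.

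**Step 2. Is this loose drafting?** Probably not. SAP 5.3 writes out the preferred-term level for the three subsets shortly after leaving it out for all TEAEs, and SAP 5.5 asks for concomitant medications by drug class and preferred term. Read literally, medications get a finer table than all-cause adverse events. SAP 5.3 shows no redaction that might hold the missing words.

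**Step 3. Follow one event.** Take a bradycardia that is non-serious and does not stop treatment.

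- Judged related: it enters the drug-related table under its preferred term.
- Judged not related: it enters no specified preferred-term table. It is counted in an organ-class total and appears in the listing.

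**Step 4. Apply this to the three examples in Protocol 5.10.**

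- *PML.* Protocol 6.11.1.1 describes it as usually fatal or severely disabling and links a confirmed case to permanent discontinuation. A confirmed case would be expected to enter the SAE and discontinuation tables, neither of which is filtered by causality.
- *Infections.* These are named as a group, which is something an organ-class count can show. Serious and discontinuing cases also get preferred-term counts.
- *Bradycardia.* This is the clearest gap in the visible text, subject to what SAP 5.8 contains.

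**Step 5. Illustrate the size on the right denominator.** The rates here are assumptions. The denominator is the safety population, meaning randomized and dosed patients. It is not the 39 evaluable patients per group in SAP 7.1, who are those with the Mayo score at baseline and Week 12. At the protocol's upper limit there are 240 / 3 = 80 patients per arm. If 10% of them had a non-serious, non-discontinuing bradycardia, that is 80 × 0.10 = 8 patients. The drug-related table would then show:

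- 25% judged related: 8 × 0.25 = 2, with 6 not shown
- 50% judged related: 8 × 0.50 = 4, with 4 not shown
- 75% judged related: 8 × 0.75 = 6, with 2 not shown

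This shows undercounting within one arm, and nothing about a difference between arms.

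**The case against.** The strongest reply is that the SAP never says all-cause events are tabulated *only* by organ class. It says events are coded and tabulated, leaves the level of two summaries open, and presents the subset tables as additions. Every TEAE is listed with its treatment, so nothing is lost, and heart rate is summarized by arm among the vital signs. On this view the matter could be settled in the table shells.

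Part of this stands. No data are lost, and a programmer could produce the fuller table unasked. But a listing is not a pre-specified incidence, a mean change in heart rate is not a count of patients with an event, and the one sentence that gives a level for all TEAEs stops at organ class.

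A reader might infer three stronger things that the documents do not support.

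- *That the special-interest events get no all-cause incidence by arm.* Serious and discontinuing cases do get one, infections are named as a group, and the SAP text that is not visible may cover bradycardia. Protocol 5.10 also gives these events as examples within the DSMB's remit, under a separate charter. It does not promise a table in the study report.
- *That the comparison between arms would be biased.* Investigators are blinded (Protocol 5.8.2), so causality judgements need not differ by arm. Protocol 6.11.4 also defines a related event broadly, to include some that other causes could explain, so a low related share cannot be presumed.
- *That the choice between 1 mg and 2 mg rests on these rates.* No passage says so.

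**Conclusion.** The point holds as a limited gap in reporting. As written, SAP 5.3 and Protocol 9.8.1 provide no by-arm preferred-term count of all TEAEs. What goes uncounted at that level is the set of events that are non-serious, do not end treatment and are judged unrelated; the total all-cause incidence of any single term is therefore also missing from the specified tables.

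The number of patients affected cannot be derived from the documents, because they give neither event rates nor the share judged related. The consequence is incomplete counts. Bias between arms is not shown.

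The conclusion on the all-TEAE table rests on SAP 5.3 alone, which shows no redaction. The conclusion on the special-interest events is limited to visible text and would fall away if SAP 5.8 or the blacked-out entry after it already summarizes them.

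**What to change.** In SAP 5.3, change the all-TEAE table to read: *by system organ class and preferred term, by treatment group, regardless of relationship*, shown as number (%) of patients in the safety population.

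Then check the SAP sections that are not visible. If none already does so, add a by-arm number (%) summary of the events named in Protocol 5.10, with the preferred terms that make up each event fixed before unblinding.

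No between-group confidence interval is needed for these tables, since SAP 5 limits adverse events to summary tabulations.

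The cost is one or two extra tables from data already coded in MedDRA. There is no new data collection and no change to trial conduct. Protocol 9 leaves analysis detail to the SAP, so a SAP edit should be enough.
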